### 9.1 Objectives

The primary objectives of this phase II study are: 1) to examine the **feasibility** of a prospective multi-institutional study of TOS followed by risk-adjusted adjuvant therapy in this patient population; and 2) to assess the oncologic **efficacy** of the proposed treatment strategy (TOS + reduce dose radiotherapy) for the intermediate risk group. The accrual rate, patient risk distribution (especially the proportion of the intermediate risk group), and surgical quality are used to evaluate feasibility of the study. The 2-year progression-free survival (PFS) rate will be used to evaluate the efficacy in the intermediate risk group. The table below gives a summary of the stopping rules / decision rules to be implemented with regard to these two primary objectives. Details are given in following sections.

Rev. 2/15

Objective	Endpoint	Assessment Time point	Suspension rules / Decision Rules
Efficacy	1-year PFS rate	First 10 patients in arm A followed for 1 year	Currently enrolled and subsequent patients who have not progressed will receive radiotherapy 50 Gy if 2 or more patients progress or die within 1 year
	1-year PFS rate	First 10 patients with p N2C/N3 disease followed for 1 year	Currently enrolled and subsequent patients with p N2C/N3 disease who have not progressed will receive IMRT 66 Gy + cisplatin (Arm D treatment) if 2 or more patients progress or die within 1 year
	1-year PFS rate	First 40 patients in each of arms B and C followed for 1 year	Suspend trial and review if $\geq 6$ patients (per arm) progress or die within 1 year
	2-year PFS rate	End of study	Treatment worthy of further study if higher limit of the 90% CI $> 85\%$
Feasibility	Accrual	13-18 months post-activation	Accrual will be monitored by DSMC and NCI (see section below)
	Risk distribution	First 59 patients evaluated for risk	Suspend trial and review if $\leq 21$ patients with intermediate risk
	Surgical quality	First 59 patients completed transoral resection and have CTCAE forms submitted	Suspend trial and review if $\geq 13$ patients reported with grade 3-4 bleeding or positive margins

Secondary objectives include assessing quality of life (QOL) and swallowing function before and after treatment, evaluating toxicity, and investigating the prognostic effects of various biomarkers (details follow).

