To safeguard against an unacceptably high failure rate for Arm B and Arm C, in which both the radiation dose is reduced and chemotherapy is removed, an interim look at 1-year PFS rate will be performed for the first 40 eligible and treated patients in Arm B and Arm C, separately. It is expected, for either arm, 90% of patients will be alive and progression free at 1 year (Fakhry, C, JNCI, 2008). The event rate will be deemed too high if 6 or more such events are observed within 1 year, which corresponds to an empirical progression rate of 15%. In this case, the trial will be suspended and a panel review will be called. The following table summarizes the probability of suspending the trial under various true 1-year progression rates in Arm B (and Arm C). For instance, the probability of suspending the trial is at least 84% if the true 1-year progression rate is 20% or higher. The study will continue accrual while we are waiting for the decision from this interim analysis.

True 1-yr progression rate for patients with intermediate risk	0.10	0.15	0.20	0.25	0.30
Probability of suspending the trial	0.21	0.57	0.84	0.96	0.99

Similarly, to safeguard against an unacceptably high failure rate for the observational Arm A, an interim look at 1-year PFS rate will also be performed for the first 10 eligible and treated patients (a total of 38 patients is expected to be accrued to this arm). Among these 10 patients, if 2 or more patients progressed or died within 1 year, currently enrolled and subsequently enrolled low risk patients who have not progressed will be directly assigned to radiotherapy IMRT 50 Gy. The same interim monitoring rule will be applied to the patients with pathological N2C/N3 disease who are directly assigned to Arm C (expected to be 5% of the total population). That is, if 2 or more patients among the first 10 such patients progress or die within the first year, currently and subsequently enrolled patients with p N2C/N3 disease will be treated with IMRT 66 Gy + cisplatin (Arm D treatment). The following table summarizes the probability of observing 2 or more events, under various true 1-year PFS rate for this group of patients.

True 1-yr PFS rate	0.10	0.15	0.20	0.25	0.30
Probability of observing 2 or more events	0.26	0.46	0.62	0.76	0.85

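### Section 9.3 interim tables: one-arm probabilities are labelled as trial-level suspension probabilities (0.21 printed; 0.37 if either arm suspends), and an event-rate axis is labelled as PFS

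*Combined protocol and SAP*

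**What the plan says.** In Section 9.3, under the interim analysis of 1-year PFS, the plan calls for a look "for the first 40 eligible and treated patients in Arm B and Arm C, separately". The planning expectation is favourable: "It is expected, for either arm, 90% of patients will be alive and progression free at 1 year". Six or more events count as too many, and the consequence falls on the study as a whole: "In this case, the trial will be suspended and a panel review will be called". The decision-rule table in Section 9.1 repeats this, with suspension and review as the action once 6 or more "patients (per arm) progress or die within 1 year".

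The operating characteristics are introduced by "The following table summarizes the probability of suspending the trial under various true 1-year progression rates in Arm B (and Arm C"). The row is labelled as the probability of suspending the trial and reads 0.21, 0.57, 0.84, 0.96 and 0.99 at true 1-year progression rates of 0.10, 0.15, 0.20, 0.25 and 0.30. The worked example uses the same trial-level wording: "For instance, the probability of suspending the trial is at least 84% if the true 1-year progression rate is 20% or higher".

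A second rule, 2 or more events among the first 10 patients, covers Arm A and, separately, the pathologic N2c/N3 patients assigned to Arm C. Its table is introduced by "The following table summarizes the probability of observing 2 or more events, under various true 1-year PFS rate for this group of patients". The axis, also labelled as a 1-year PFS rate, runs 0.10 to 0.30, with entries 0.26, 0.46, 0.62, 0.76 and 0.85.

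**The concern.** Two labels do not match the numbers beneath them.

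First, two arms each get a chance to trigger a suspension of the trial, yet the row labelled at trial level looks like the result for a single arm. If so, it understates how often a trial performing as planned would be suspended. The plan also does not say in words whether one arm crossing is enough.

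Second, the Arm A and N2c/N3 table, read as labelled, says that 2 or more events become more likely as PFS improves. It then gives no figure for a group doing well, which is the case where one most wants the false-alarm rate.

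These tables are the plan's only statement of how its interim safety rules behave, and a monitoring committee would rely on them when interpreting a crossing.

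**Working it through.** **Inputs.** From Section 9.3: 40 patients per arm, limit 6 events, arms looked at separately, expected 1-year event rate 1 − 0.90 = 0.10 in either arm; and 10 patients with limit 2 events for the second rule. Section 9.1 gives the same limits.

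**Step 1: reproduce the Arm B/C row.** With X ~ Binomial(40, p), the one-arm crossing probability is q = P(X ≥ 6).

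| True 1-year event rate p | 0.10 | 0.15 | 0.20 | 0.25 | 0.30 |
|---|---|---|---|---|---|
| Printed | 0.21 | 0.57 | 0.84 | 0.96 | 0.99 |
| q, one arm | 0.2063 | 0.5675 | 0.8387 | 0.9567 | 0.9914 |

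All five agree after rounding, so the row is a one-arm probability.

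**Step 2: trial-level probability under each two-arm reading.** The arms hold different randomized patients, so independence is reasonable. The same true rate is assumed in both arms.

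| Reading | Formula | 0.10 | 0.15 | 0.20 | 0.25 | 0.30 |
|---|---|---|---|---|---|---|
| Either arm crosses | 1 − (1 − q)² | 0.3700 | 0.8129 | 0.9740 | 0.9981 | 0.9999 |
| Both arms must cross | q² | 0.0425 | 0.3221 | 0.7034 | 0.9153 | 0.9828 |
| Pooled, 12 or more of 80 | Binomial(80) tail | 0.1004 | 0.5478 | 0.8994 | 0.9894 | 0.9994 |

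At p = 0.10 the either-arm figure is 1 − (1 − 0.2063)² = 0.370, and 0.370 / 0.2063 = 1.79 times the one-arm value. A pooled limit of 6 of 80 gives 0.823 at 0.10. None of these readings gives the printed row.

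**Step 3: where the 0.37 comes from.** Exactly one arm crosses with probability 2q(1 − q) = 2 × 0.2063 × 0.7937 ≈ 0.33; both cross with probability q² ≈ 0.04. Most of the total therefore depends on whether a single arm is enough.

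**Step 4: sensitivity to the assumptions.** Without independence, the either-arm probability at 0.10 lies between q = 0.21 and 2q = 0.41. With one arm at 0.10 and the other at 0.15, it is 1 − 0.7937 × 0.4325 = 0.66; with the other at 0.20, it is 0.87.

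**Step 5: the second table.** With X ~ Binomial(10, p), P(X ≥ 2) = 1 − (1 − p)¹⁰ − 10p(1 − p)⁹.

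| Axis value | 0.10 | 0.15 | 0.20 | 0.25 | 0.30 |
|---|---|---|---|---|---|
| Printed | 0.26 | 0.46 | 0.62 | 0.76 | 0.85 |
| Axis taken as event rate | 0.2639 | 0.4557 | 0.6242 | 0.7560 | 0.8507 |
| Axis taken as PFS (event rate = 1 − axis) | >0.9999 | >0.9999 | >0.9999 | >0.9999 | 0.9999 |

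The entries match an event-rate axis. On the printed label, the smallest value, at PFS 0.30 (event rate 0.70), would be 1 − 0.3¹⁰ − 10 × 0.7 × 0.3⁹ = 0.99986.

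**The case against.** The strongest reply is that nothing is miscalculated and the context supplies the missing words. The look is described as separate for each arm, the expectation is stated for either arm, the lead-in names Arm B with Arm C in brackets, and Section 9.1 says per arm. Section 9.3 presents results arm by arm elsewhere too. On that view the row is the chance that the rule fires in a given arm, and suspension is simply what then follows. The worked sentence also remains true as a lower bound: if one arm has a 20% rate, suspension is at least 84% likely whatever the other does. The 0.37 rests on an either-arm rule that the plan leaves to inference.

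The practical effect is also limited. A crossing leads to suspension and panel review, not termination, and accrual continues while the interim decision is awaited. A rough projection from the plan's figures points the same way. About 104 × 0.48 ≈ 50 intermediate-risk patients were evaluable at the Fall 2015 analysis, and they accrue at about 18.5 × 0.35 ≈ 6.5 per month. Eighty would be reached in early 2016 and followed for a year by early 2017, close to the projected end of accrual in February 2017. As for the second table, the surrounding text refers to patients who progressed or died, so the intended axis can be recovered.

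These points stand, and they limit the seriousness. They do not make the labels right. The row label and the worked sentence both refer to the trial, and no trial-level figure appears anywhere. The second table is wrong in both its axis label and its lead-in sentence.

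**Conclusion.** The concern holds as a labelling and reporting fault that should be corrected; every printed probability is right for the quantity it actually computes.

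On the either-arm reading, with independent arms both at the plan's expected 10% event rate, the chance of suspending the trial is more than one in three rather than about one in five. The omission works in the other direction as well: with both arms at 20%, the chance of suspension is 0.97 rather than 0.84, so the rule is more sensitive than stated. The either-arm reading is an inference, but the wording of Sections 9.1 and 9.3 supports it.

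The second mislabelling needs no assumption. The entries are for 1-year progression or death rates of 0.10 to 0.30; the printed 0.26, for example, is the chance of 2 or more events when true 1-year PFS is 90%.

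**What to change.** 1. Relabel the Arm B/C row as the probability of crossing in one arm, and adjust the worked sentence to match.
2. State in words whether a crossing in one arm alone suspends the trial and calls the panel review. If it does, add a trial-level row (either arm crosses; independent arms, same true rate in both): 0.37, 0.81, 0.97, 0.998, >0.999.
3. In the Arm A and N2c/N3 table and its lead-in sentence, replace the PFS label with the true 1-year progression or death rate. Alternatively, keep PFS and print the axis as 0.90, 0.85, 0.80, 0.75, 0.70.

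The cost is a few labels and sentences and one added row. No boundary, decision rule, sample size or analysis changes. The one unwelcome consequence is a less favourable stated false-suspension probability, 0.37 in place of 0.21.

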9.4 Primary Objective: Feasibility

Three endpoints will be used to evaluate the feasibility of the proposed trial.

Rev. 2/15

### *Accrual Rate of the Entire Study*

The following monitoring plan for accrual was specified in the original design. If the accrual during quarters 5 and 6 (that is, during months 13-18 after activation) is  $\leq 20\%$  of the projected rate during that period, then the study will be terminated. If the quarter 5-6 accrual rate is  $> 20\%$  but  $< 50\%$  of the planned rate, then the study team will be given 6 months to improve accrual. If the average accrual rate in quarter 8 is still  $< 50\%$  of the planned rate, then the study design will be amended to reflect the actual accrual rate. The currently observed accrual rate is 18.5 patients per month.

### *Risk Distribution*

Given the distribution of the histologic risk is unknown, this trial provides an opportunity to find out patient distribution in each risk cohort. A 90% binomial confidence interval will be estimated for the percentage of patients in each risk group. All eligible patients on Step 2 will be analyzed. It was expected 60% patients would be intermediate risk in the original design.

An interim analysis was planned in the original design: among the first 59 patients who have completed transoral resection and have risk status evaluated, if 21 (36%) or fewer are intermediate risk, the percentage will be deemed too low. Based on results from the interim analysis, the estimated proportion for the intermediate risk category is 48%, among the 104 evaluable patients.

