## 9. Statistical Considerations

Rev. 2/15

This is a phase II trial of p16+ (using immunohistochemistry (IHC)) OPSCC patients that will undergo transoral surgery (TOS, Step 1) followed by risk-adjusted radiotherapy (Step 2). Patient risk status is determined after surgical excision and is defined in Section 5.1. Patients with low-risk will be assigned to the observation group (Arm A). Patients with intermediate-risk (the primary study group) will be equally randomized to receive radiotherapy IMRT 50 Gy (Arm B) or 60 Gy (Arm C), stratified by current/former smoking history ( $\leq 10$  vs.  $> 10$  pack-years). Patients with pathological N2C/N3 disease without extensive ECS (and do not meet the high risk feature) will be directly assigned to Arm C receiving IMRT 60 Gy. Patients with high-risk will receive concurrent cisplatin and IMRT 66 Gy (Arm D). Among the first 10 patients enrolled on Arm A, if 2 or more progress or die within 1 year, currently enrolled and subsequently enrolled patients with low risk who have not progressed will be directly assigned to radiotherapy 50 Gy (details are given below).

The study requires 180 evaluable patients with intermediate risk (to be randomized between Arms B/C). Based on results from the interim analysis prepared for the Fall 2015 DSMC meeting, the overall proportion of evaluable patients with intermediate risk is estimated to be 35% (~73% patients are evaluable, among whom ~48% are intermediate risk), which is lower than the originally estimated 48% (80% evaluable, among whom 60% would be intermediate risk). Here, patients who are eligible and started treatment on step 2 are considered as evaluable. As stated in the original design, if the observed proportion of patients with intermediate risk is off over 5% from the anticipated 60%, accrual goal would be adjusted. Therefore, the current section incorporates a sample size increase from the originally proposed 377 to 515 ( $180/0.35=515$ ), to ensure 180 evaluable patients with intermediate risk to be randomized. Based on the observed accrual rate of 18.5 patients per month, this new accrual goal can be achieved in February, 2017.

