In the original design, the risk distribution was assumed to be 10% low risk, 60% intermediate risk, and 30% high risk, and an interim analysis for the first 59 patients who complete transoral resection was scheduled. Based on the analysis results, among the 104 evaluable patients (not ineligible based on current evaluation, and started treatment on step 2), the estimated risk distribution is: 8% low risk, 48% intermediate risk and 32% high risk (13 (12%) patients had potentially misclassified risk category/ arm based on their surgical data and the study team is taking various actions trying to improve this). As was stated in the original design, in case the proportion of the intermediate risk patients is off over 5% from the anticipated 60%, the accrual goal would be adjusted, With this new accrual goal, we expect at the end of the study ~180 evaluable patients would be intermediate risk, ~120 high risk, and ~30 low risk.

In analyzing the 2-year PFS rate, 90% exact binomial confidence intervals will be computed for each arm. Only eligible patients with confirmed P16+ status who started radiotherapy will be analyzed (by arm). The regimen will be considered worthy of further study if the higher limit of the computed 90% CI exceeds 85%.

Comparisons of 2-year PFS rates between Arms B and C, Arms B and D, and Arms C and D are exploratory endpoints. Since one of the randomized arms proposed in this study is likely to be selected for a follow-up phase III study, the exploratory comparison of 2-year PFS rate between the two randomized arms is more important and a p-value  $\leq 0.05$  will be considered statistically significant. For the other two comparisons (Arms B and D; Arms C and D), the Type I error rate of 5% will be divided by the two tests (i.e., 0.05/2 considered statistically significant). Therefore, the family-wise error rate of 0.10 will be protected for the multiple comparisons in the 2-year PFS rate among arms. Power for various differences in the 2-year PFS rate is shown below, assuming a two-sided Fisher's exact test and 90 analyzable patients in Arms B or C, and 120 analyzable patients in arm D.

Difference in 2-year PFS rate between arms	Arm C vs. Arm B	Arm B (or C) vs. Arm D
10% (85% vs. 75%)	0.32	0.27
15% (85% vs. 70%)	0.62	0.58
20% (85% vs. 65%)	0.85	0.83
25% (85% vs. 60%)	0.96	0.96

*Interim Analysis—1-year PFS rate*

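### The final risk-distribution estimate in 9.4 leaves out resected patients who do not enter Step 2, although risk class is fixed by surgical pathology before that step

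*Combined protocol and SAP*

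**What the plan says.** Risk distribution is one of the three feasibility endpoints under a primary objective (2.1.1, 9.1, 9.4). The plan describes its population in three ways.

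- **Interim rule.** Section 9.4 applies it "among the first 59 patients who have completed transoral resection and have risk status evaluated, if 21 (36%) or fewer are intermediate risk". The decision table in 9.1 has "First 59 patients evaluated for risk", and 9.3 recalls that "an interim analysis for the first 59 patients who complete transoral resection was scheduled". None of these mentions Step 2.
- **Final analysis.** For the 90% binomial intervals on each risk group, 9.4 says "All eligible patients on Step 2 will be analyzed".
- **Reported interim result.** Section 9.4 states that "the estimated proportion for the intermediate risk category is 48%, among the 104 evaluable patients". The opening of Section 9 explains the term: "patients who are eligible and started treatment on step 2 are considered as evaluable".

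The neighbouring surgical-quality endpoint in 9.4 uses all eligible patients who had surgery, with no Step 2 condition.

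**The concern.** Section 9.4 gives as its reason for this endpoint that the distribution of histologic risk is not known. That distribution belongs to operated patients. Margins, extracapsular extension, nodal findings and perineural or lymphovascular invasion are all settled by the surgical specimen. Step 2 registration comes later (up to 7 weeks after surgery, 3.2.3) and leads to observation, randomised radiotherapy or chemoradiation according to class. Whether a patient goes on may therefore depend on the class being estimated. If so, a distribution taken only from patients who went on is a selected one.

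The plan foresees such patients. Table 3 in 7.1, the sample table in 7.2 and Appendix V all make arrangements for Arm S patients who do not register to Step 2. Nothing in 9.4 says why they are left out of the risk distribution. At stake is an estimate that is meant to inform a later phase III design (1.3): a planner would read it as the mix to expect after transoral surgery.

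**Working it through.** **1. The plan's own figures reproduce.**
- Opening of Section 9: "73% patients are evaluable, among whom ~48% are intermediate risk". 0.73 × 0.48 = 0.350, and 180 / 0.35 = 514.3, printed as 515.
- 9.2: 515 × 0.73 = 376 evaluable, and 376 × 0.48 = 180 intermediate.
- 9.4: 21/59 = 35.6%, printed as 36%.
- 9.3 and 9.4: 48% of 104 is 50 patients (50/104 = 48.1%). The exact 90% interval is 39.7% to 56.6%.

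**2. How many patients could be missing.** The documents do not say how many resected, classifiable patients lie outside the 104. Assume that the approximate 73% applies to the same cohort. Then 104 / 0.73 ≈ 142 registered, and 142 − 104 = 38 were not evaluable. These 38 can include ineligible patients and patients never resected, so 38 is a ceiling.

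**3. Bounds on the intermediate share.** Let k of the omitted patients be eligible, resected and classifiable. The share among all such patients lies between 50/(104 + k), if none of the k is intermediate, and (50 + k)/(104 + k), if all are.

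| k (assumed) | Lower bound | Upper bound |
|---|---|---|
| 10 | 50/114 = 43.9% | 60/114 = 52.6% |
| 19 | 50/123 = 40.7% | 69/123 = 56.1% |
| 38 (ceiling) | 50/142 = 35.2% | 88/142 = 62.0% |

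**4. The same bounds at the planned final size.** Take the 376 evaluable patients as a stand-in for the Step 2 set. 180/376 = 47.9%, with exact 90% interval 43.5% to 52.2%. Up to 515 − 376 = 139 patients are outside.
- 40 omitted but classifiable: 180/416 = 43.3% to 220/416 = 52.9%.
- 60 omitted but classifiable: 180/436 = 41.3% to 240/436 = 55.0%.
- All 139: 180/515 = 35.0% to 319/515 = 61.9%.

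At the interim, the bounds for k = 10 and k = 19 sit inside the sampling interval. At the final size, omitting 40 already gives bounds slightly wider than that interval. Sampling error shrinks as patients accrue; a selection effect need not.

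**The case against.** The strongest reply is that formal risk assignment takes place at Step 2 (3.2.2 and 4.2.4.1), so a patient whose risk has been evaluated may simply mean a patient classified at Step 2, and all classes, including low-risk observation, register there. That may explain the choice. It does not make Step 2 entrants representative of operated patients, and the pathology that defines the class exists beforehand.

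It is also fair to say that no dependence of Step 2 entry on class is shown: the documents give no reasons for non-entry by risk group. This stands, and the point is a possible bias, not a demonstrated one. Another uncertainty lies inside the 104. Section 9.3 sets 13 patients (12%) apart as potentially misclassified, and since 8 + 48 + 32 + 12 = 100, the 48% counts none of them as intermediate. Were all 13 intermediate, the share would be 63/104 = 60.6%.

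Three stronger readings may tempt a reader.

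- *That the 48% was tested against the suspension boundary in the wrong population.* Section 9.4 prints the 48% after describing the rule but never says that the rule was applied to the 104. The documented use of the figure is the accrual adjustment.
- *That the true share may be below the 36% boundary.* The 35% case needs all 38 omitted patients to be eligible, resected and classifiable, and none of them intermediate. It also sets a share of 142 patients against a rule written for 59.
- *That the accrual goal is wrong.* It is not. The goal needs the joint yield of evaluable and intermediate patients, and loss before Step 2 is already in the 73%.

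**Conclusion.** The point holds as an inconsistency of analysis population with a possible selection bias of unknown size and direction. The final estimate is restricted to Step 2 patients, the interim rule is written for resected patients, and the reported interim figure uses a third, narrower set. Under the stated assumptions, moderate omission (10 or 19 patients) would bound the intermediate share by 44–53% or 41–56%, against 48%. The 35–62% range is an outer limit and not a prediction. These ranges rest on applying the 73% to the cohort of 104 and on assumed values of k.

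No printed number needs correction. The 515 goal and the progression-free survival analysis are not affected. The change is still worth making, because this is part of a primary objective and a population closer to the stated aim is available at little cost.

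**What to change.** In 9.4, replace "All eligible patients on Step 2 will be analyzed" with a statement that the risk distribution and its 90% intervals will be estimated in all eligible patients who completed resection and whose risk class can be derived from the submitted pathology and surgical reports, whether or not they register to Step 2. Count patients who cannot be classified as a separate category. Report the distributions among Step 2 registrants and among those who started Step 2 treatment as secondary yields, labelled as such.

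The 59-patient interim rule needs no redefinition: interim results have been reported, and rewording the rule now would change no decision.

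The cost is one sentence and some classification work. The reports are mandatory for all patients (7.2, 11.1.1, 11.2.1) and must give margin status, extracapsular extension, and perineural and lymphovascular invasion. Some may be missing: the surgical-quality text in 9.4 mentions 10 early patients with no surgical data. That is why the unclassifiable category is needed.
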